Effectiveness of Salbutamol Administration by Nebulizer versus Metered Dose Inhaler in Acute Asthma in Children in Suez Canal University Hospital Emergency

Department: A Randomized Control Trial

March 10th 2018

Study Protocol

Study design

Single-blinded randomized control trial.

Study location

Pediatric Emergency Department in Suez Canal University Hospital.

Study population

This study includes patients presenting with an acute exacerbation of asthma at the Pediatric Emergency Department in Suez Canal University Hospital.

Inclusion criteria:

- Children ranging from 2 – 14 years old.
- Both genders will be included.
- Patients with an acute exacerbation of asthma who were previously diagnosed with asthma.

Exclusion criteria:

- Patients with arrhythmia and cardiac diseases.
- Patients with thyroid diseases.
- Patients with bronchiolitis or pneumonia.
- Patients with status asthmaticus requiring immediate pediatric intensive care unit hospitalization.

Sampling

All children fulfilling the inclusion criteria will be included consecutively until the calculated sample size had been reached.

Sample size

The sample size was calculated using the following formula:

$$n = 2 \left[\frac{(Z_{\alpha/2} + Z_{\beta}) * \sigma}{\mu_1 - \mu_2} \right]^2$$

Where:

n = sample size

$Z_{\alpha/2} = 1.96$ (The critical value that divides the central 95% of the Z distribution from the 5% in the tail)

$Z_{\beta} = 0.84$ (The critical value that separates the lower 20% of the Z distribution from the upper 80%)

σ = the estimate of the standard deviation = 1.5

μ_1 = mean in the nebulizer group = 4.4

μ_2 = mean in the metered-dose inhaler group = 3.3

Therefore, by calculation, the sample size was equal to 30 cases per group, giving a total sample size of 60 cases.

Methods of data collection

Infants and children known to have asthma coming to the Pediatric Emergency Department of Suez Canal University Hospital and fulfilling the inclusion criteria will be assessed according to the following clinical respiratory score:

Assess	Score 0	Score 1	Score 2
Respiratory Rate	<2 months <50 2-12 months <40 1-5 years <30 >5 years <20	<2 months 50-60 2-12 months 40-50 1-5 years 30-40 >5 years 20-30	<2 months >60 2-12 months >50 1-5 years >40 >5 years >30
Auscultation	Good air movement, expiratory scattered wheezing or loose rales/crackles	Depressed air movement, inspiratory and expiratory wheezes or rales/crackles	Diminished or absent breath sounds, severe wheezing, or rales/crackles or marked prolonged expiration
Use of Accessory Muscles	Mild to no use of accessory muscles, mild to no retractions OR nasal flaring on inspiration	Moderate intercostals retractions, mild to moderate use of accessory muscles, nasal flaring	Severe intercostals and substernal retractions, nasal flaring
Mental Status	Normal to mildly irritable	Irritable, agitated, restless	Lethargic
Room Air SpO2	> 95%	90-95%	<90%
Color	Normal	Pale to normal	Cyanotic, dusky

[figure not shown]
(Mild 0-3 moderate 4-7 severe 8-12)

The target population are patients who presented with moderate to severe wheezing (score 4-12).

Randomization will take place through a box that contained 60 thick envelopes, in which either nebulizer or spacer are written on 30 each, and each time an envelope is picked out by the assistant nurse in the emergency room to avoid any selection bias till our sample is fulfilled.

The assessment of the respiratory score before and after the treatment will be performed by an independent pediatrician resident who isn't involved in the decision-making and randomization of treatment. This physician will be asked to assess initially and then reassess after the equipment had been removed to avoid any bias.

CONSORT Flow Diagram to be filled in during the study:

Dosage and administration:

The nebulizer group will receive salbutamol aerosol solution (Farcolin® 0.121 gm/20ml solution) in a dose of 0.15 mg/kg weight, up to a maximum of 5 mg in 3.5 ml of normal saline solution. Aerosol is generated by jet nebulizers (Afnor oxygen flow meter) powered by oxygen and delivered via a face mask till the whole solution is vaporized every 20 min during the first hour (a maximum of three nebulization /hr). A flow rate of 7 L/min is used. (Liu, Covar, and Leung, 2016)

The metered dose inhaler with spacer group will receive two puffs of salbutamol (Ventolin® evohaler 100 mcg/puff) every 10 min 5 times over 1 hr with a maximum of 10 puffs/hr, using a spacer device with a face mask (Smart care chamber 500ml volume). Following each puff, the children will take 7 breaths from the spacer device held in place. (Rubilar, Castro-Rodriguez and Girardi, 2000)

Assessment:

Patients will be reassessed after each treatment, if improved we can stop treatment and follow up after 2 hrs. Score <4 is considered a success while score>4 is failure of therapy. If not improved, we continue till the maximum number of treatment mentioned above.

Patients will be compared together according to the following characteristics: duration of treatment (preparation and delivery time), clinical outcome, patient satisfaction after treatment and hospitalization rate.

Each patient will have a form: Page 1 is an informed consent to be signed before randomization of treatment. Page 2 includes the following items that will be filled by parents after receiving the treatment;

1-personal data (name, age, address and telephone number). In addition, the researcher's phone number will be accessible to the patients.

2- Medical history (other illnesses, medications and degree of asthma either intermittent or persistent)

3-Clinical assessment (clinical respiratory score before and after treatment)

4-Patient satisfaction with given modality on a Likert scale from 1-5. This will be asked by the blinded assessor and included questions regarding:

- Comfort with modality used
- Duration of modality used
- Ease of administration
- Confidence in repeating treatment on their own at home if required

Statistical analysis of the data (Kotz et al, 2006)

Data will be fed to the computer and analyzed using IBM SPSS software package version 20.0. (Armonk, NY: IBM Corp) (Kirkpatrick, Feeney, 2013). Qualitative data will be described using number and percent. The Kolmogorov-Smirnov test is used to verify the normality of distribution. Quantitative data will be described using range (minimum and maximum), mean, standard deviation and median. Significance of the obtained results will be judged at the 5% level.

The used tests will be

1 - Chi-square test

For categorical variables, to compare between different groups (gender, address, satisfaction, admission)

2 - Fisher's Exact or Monte Carlo correction

Correction for chi-square when more than 20% of the cells have expected count less than 5

3 - Student t-test

For normally distributed quantitative variables, to compare between two studied groups (delivery and preparation time)

4 - Mann Whitney test

For abnormally distributed quantitative variables, to compare between two studied groups (age, percentage of improvement of clinical respiratory score and satisfaction).

Ethical Considerations

- An informed consent will be obtained from legal guardian of all patients included in this study after full explanation of the aim of the study, benefits and hazards of the procedures.
- Standardized protocols are used for evaluation.
- The legal guardians have the right to withdraw without affecting the medical care expected to be offered to them.
- Confidentiality of all data and test results of all the study population will be preserved.
- The new modality introduced is a well-established form of administration and is not expected to cause any side effects that would not happen with the standard mode of administration (nebulizer).

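### Allocation by drawing envelopes from a box in the emergency room does not secure the claimed protection from selection bias, because no stated step ties an envelope to a child or records the draw

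*Combined protocol and SAP*

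**What the plan says.** The only description of randomization is one paragraph under Methods of data collection. It specifies "a box that contained 60 thick envelopes, in which either nebulizer or spacer are written on 30 each" and adds that "each time an envelope is picked out by the assistant nurse in the emergency room to avoid any selection bias", until the sample is complete. The draw itself is the randomization; no separate list or sequence is mentioned.

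Safeguards stated elsewhere:

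- Consent (Assessment): "Page 1 is an informed consent to be signed before randomization of treatment".
- Enrolment (Sampling): "All children fulfilling the inclusion criteria will be included consecutively until the calculated sample size had been reached".
- Scoring (Methods of data collection): before and after treatment, by an "independent pediatrician resident who isn't involved in the decision-making and randomization of treatment".
- Design label (Study design): "Single-blinded randomized control trial".

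The patient form described under Assessment has a consent page and a second page with personal data, history, the respiratory score before and after treatment, and satisfaction. That second page is described as completed after treatment. No envelope number and no draw date or time is listed.

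**The concern.** The plan claims a specific protection, so the question is whether the written procedure delivers it. Concealment by envelope works when the next allocation is fixed in advance and cannot be exchanged once seen. A draw from a box fixes nothing in advance. If the nurse, or someone the nurse consults, sees an unwelcome device for a particular child, the envelope can go back and another can come out. Nothing described in the plan would register this.

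The draw takes place in the treating department, severity is visible, and eligible scores run from 4 to 12. Ethical Considerations treats the nebulizer as the standard mode and the inhaler as the new one, so a preference for the familiar device in sicker children is conceivable. The documents give no sign that anyone holds it.

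If sicker children were steered to one device, the arms would differ at baseline. The tests under Statistical analysis of the data are all unadjusted two-group comparisons, and none uses the baseline score as a covariate. Hospital admission and success defined as a score below 4 both depend on how ill the child was at the start, so they are the most exposed. Percentage improvement in the score is taken relative to each child's own starting value and is less directly affected.

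**Working it through.** **The plan's own figure.** From Sample size: SD 1.5, means 4.4 and 3.3, Z values 1.96 and 0.84. n = 2 × [(1.96 + 0.84) × 1.5 / 1.1]² = 29.16, rounded up to 30 per group. The total of 60 matches the number of envelopes. This point does not affect the sample size.

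**Each safeguard against an untraced redraw.**

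- Thick envelopes hinder reading the contents through the paper. They do not stop one being opened and replaced.
- Consent first does not fix which envelope is used.
- Consecutive enrolment governs who enters, not which arm they enter.
- The independent assessor protects the scoring, not the draw.
- The form, as listed, does not connect a child to an envelope.

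**Illustration of size.** None of these inputs is in the documents except the 60 envelopes, the 30/30 split and the SD of 1.5: the proportion p of severe children is 30% or 50%; severity adds 1.5 points (1 SD) to the outcome; there is no device effect; a spacer draw for a severe child is returned and redrawn once with probability q. There were 6,000 simulated trials per row, analysed with a two-sided 5% t-test.

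As a check, let s be the shift in the share of severe children (nebulizer minus spacer). Then δ = 1.5s / [σ√(2/30)] with σ² = 1.5² + 1.5²p(1 − p), and the rejection rate is approximately Φ(−1.96 + δ) + Φ(−1.96 − δ). For p = 0.3, σ = 1.65 and the standard error is 0.426. For p = 0.5, σ = 1.677 and the standard error is 0.433.

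| p | q | s | δ | Rejection, simulated | Rejection, formula |
|---|---|---|---|---|---|
| 0.3 | 0 | −0.001 | 0 | 4.9% | 5.0% |
| 0.3 | 0.25 | 0.049 | 0.17 | 5.8% | 5.3% |
| 0.3 | 0.5 | 0.098 | 0.35 | 6.6% | 6.4% |
| 0.3 | 1 | 0.193 | 0.68 | 10.4% | 10.4% |
| 0.5 | 0 | −0.001 | 0 | 5.2% | 5.0% |
| 0.5 | 0.25 | 0.058 | 0.20 | 5.8% | 5.5% |
| 0.5 | 0.5 | 0.114 | 0.40 | 6.6% | 6.8% |
| 0.5 | 1 | 0.218 | 0.76 | 11.8% | 11.7% |

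The simulation error is about √(0.05 × 0.95 / 6000) = 0.3 percentage points, so the two columns agree within noise. Every simulated trial ended 30/30, which shows that the final arm counts carry no information about returned envelopes.

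**Guessability, a smaller matter.** With 30/30 drawn without replacement, someone who tracks past draws and always guesses the commoner remaining device is right about 34.4 times in 60 (57%), against 30 by chance. On average about 2 final draws are fully determined (60/31 = 1.94).

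**The case against.** The strongest reply is that the plan is brief rather than defective: it never says that envelopes are unnumbered, unsealed or unlogged, or that one may be put back. That is right as far as it goes. A reader might infer unnumbered envelopes, but the documents support only that numbering, sealing and logging are not stated. The point survives because the plan describes a specific act, picking from a box, and credits that act with preventing selection bias.

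Second, scoring probably precedes the draw, since a score of 4–12 defines the target population and the scorer has no part in randomization. This stands, and it weakens any suggestion that the envelope is drawn before severity is settled. It does not prevent a redraw afterwards.

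Third, steering by severity would not be wholly invisible. Pre-treatment scores are collected, so heavy steering would tend to appear as a baseline imbalance between arms. That also stands. What cannot be seen is the individual redraw, and an imbalance in 60 children could not be told apart from chance.

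Fourth, the effect could be made to look much larger than is warranted. Exchanging a child scoring 9 for one scoring 5 moves the difference in baseline means by 2 × 4/30 = 0.27 points, so three exchanges give 0.80, or 73% of the 1.1-point planning difference. The documents do not support that comparison. They never name the outcome behind the 1.1, and the planned score test is on percentage improvement, so a baseline shift does not carry through point for point. Nor are three net exchanges a light breach. If the exchanged children are one severe and one not, three exchanges shift the severe share by 3 × 2/30 = 20 percentage points, which the illustration reaches only when every unwanted draw is returned. That takes on average about 10 returned envelopes at 30% severe, or 18 at 50%. At the assumed 1.5 points, 20 percentage points is 0.20 × 1.5 = 0.30 outcome points.

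**Conclusion.** The concern holds as a gap in the allocation procedure. As written, nothing fixes the order of envelopes, ties one to a child or records the draw, so the claimed freedom from selection bias is not secured.

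The possible consequence is modest under light misuse and material under systematic misuse. Against a nominal 5%, the false-positive rate is about 5–6% with a quarter of unwanted draws redrawn, 6–7% with half, and 10–12% with all. These figures depend on an assumed severity effect of 1.5 points, 30% or 50% severe children, and a single redraw always favouring the same device. They apply to an unadjusted comparison of an outcome that depends on severity.

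A reader might also infer that redraws would happen, or that the nurse prefers a device. The documents say neither. The reason to act before enrolment is that an undetected redraw cannot be identified or corrected afterwards.

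**What to change.** Keep the 30/30 split. Have a person not involved in enrolling or treating the children generate a random order by computer and place the allocations in sealed, opaque envelopes numbered 1–60. The nurse opens the next number in sequence, and only after consent (already required), eligibility and the baseline score have been written down. The envelope number, date and time of opening go on the child's form.

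The cost is a short preparation task for someone outside the treating team, one extra form entry and a revised randomization paragraph. The sample size and the clinical procedures do not change. The limited guessability of a fixed 30/30 split remains; the change addresses the exchange of envelopes, which is the larger weakness.

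### The success/failure rule leaves a score of exactly 4 unclassified, although 4 is a moderate score and the lowest score at entry

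*Combined protocol and SAP*

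**What the plan says.** The score table under Methods of data collection has six items (respiratory rate, auscultation, accessory muscles, mental status, oxygen saturation, colour), each rated 0, 1 or 2. The total is banded as "Mild 0-3 moderate 4-7 severe 8-12". On entry, the same section states: "The target population are patients who presented with moderate to severe wheezing (score 4-12").

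The Assessment section gives the only numerical threshold for response: "Score <4 is considered a success while score>4 is failure of therapy". That sentence follows a treatment instruction, "if improved we can stop treatment and follow up after 2 hrs", and is followed by the instruction to carry on to the maximum number of treatments in children who have not improved. The section then names clinical outcome as one of the between-group comparisons, without saying whether this means success/failure, change in score, or both. The patient form records the "clinical respiratory score before and after treatment".

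Under Statistical analysis of the data, "Qualitative data will be described using number and percent". The chi-square list covers gender, address, satisfaction and admission. The Mann-Whitney list covers age and "percentage of improvement of clinical respiratory score and satisfaction".

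**The concern.** A rule that sorts patients into success and failure should place every attainable score. This one misses a value in the middle of the range that matters: the first score above the mild band and the lowest score at entry. A child who starts at 4 and is still at 4 after treatment has not changed and still meets the entry criterion, but the written rule does not call that child a failure. It does not call the child a success either.

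If success and failure are reported as number and percent, the two percentages will not add to 100% whenever a child ends at 4. Someone will then have to decide, possibly with the results in view, what to do with those children. At the bedside, staff have no stated class for a child at 4, because the plan gives no numerical meaning to improvement elsewhere.

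**Working it through.** **1. Coverage of the rule.** Six items rated 0-2 give whole totals from 0 to 12.

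| Final score | Severity band | In the entry range? | Class under the written rule |
|---|---|---|---|
| 0-3 | mild | no | success |
| 4 | moderate | yes (lowest value) | none |
| 5-7 | moderate | yes | failure |
| 8-12 | severe | yes | failure |

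The success class coincides with the mild band. The failure class matches the moderate and severe bands except that 4 is missing. No other sentence assigns 4. This step needs no assumption.

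**2. Does the sample size depend on the rule?** The plan's formula with its own inputs (Sample size section: Z values 1.96 and 0.84, SD 1.5, means 4.4 and 3.3) gives 2 × [(1.96 + 0.84) × 1.5 / (4.4 − 3.3)]² = 2 × (4.2 / 1.1)² = 29.16, rounded up to 30 per group. This reproduces the stated figure. It rests on a difference in means and does not use the success/failure rule.

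**3. Illustration of how many children could be at 4.** The Sample size section does not say which variable the means and SD describe. Assume, for illustration only, that they are final scores, normally distributed and rounded to whole numbers. Then P(score = 4) = Φ((4.5 − m)/SD) − Φ((3.5 − m)/SD). With SD 1.5:

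| | Nebulizer (m = 4.4) | Inhaler (m = 3.3) |
|---|---|---|
| Score below 4 | 0.274 | 0.553 |
| Score exactly 4 | 0.252 | 0.235 |
| Score above 4 (failure as written) | 0.473 | 0.212 |
| Score 4 or more | 0.726 | 0.447 |

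- Children at exactly 4: 30 × (0.252 + 0.235) = 14.6 of 60, about 24%.
- Reported failure, nebulizer vs inhaler: 47% vs 21% as written, 73% vs 45% with 4 included.
- Failure difference: 26 points as written, 28 with 4 included.

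With SD 1.0 the two-arm share at 4 is (0.356 + 0.306)/2 = 0.331. With SD 2.0 it is (0.194 + 0.186)/2 = 0.190. At SD 1.0 the failure difference is 34.5 points as written and 39.5 with 4 included, so the effect on the between-group difference is not negligible across the whole range.

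The model ignores the option to stop once a child improves, which would change the distribution of final scores.

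**The case against.** The strongest reply is that nothing planned depends on the failure class. Success/failure is not in the chi-square list, the only score variable with a listed test is percentage improvement, and the sample size uses means. The sentence sits between two treatment instructions, so it may be bedside guidance only, in which case there may be no failure count to report. Success is also fully defined: reporting successes out of 30 per group needs no change, and the bands make 4 or more the obvious meaning of failure. Finally, the sign might have been meant as ≥ and lost in typesetting or conversion.

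Most of this stands, and it limits the consequence. It does not close the gap. The sentence uses the language of outcome, clinical outcome is a named comparison, and even as bedside guidance it gives no class to a child at 4. That 4 or more was intended is a reasonable inference from the bands, but the text does not say so. Nothing in the text shows that a symbol was lost.

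A reader might go further and infer that unchanged children are being counted as successes, or that the treatment comparison is biased. The documents support neither. A 4 falls outside both classes. The largest distortion one could construct, dropping the 4s from the denominator, is not proposed anywhere in the plan.

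**Conclusion.** The point holds as a minor defect in a stated threshold: a score of exactly 4 is neither success nor failure, although the plan itself treats 4 as moderate and eligible. This rests on the text alone. It affects any failure number or percentage reported under clinical outcome, and the bedside threshold. That the rule will be used in reporting at all is an inference, because the plan does not define clinical outcome.

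How many children are involved cannot be derived from the documents. The figure of about 24% (19% to 33% for an SD of 2.0 down to 1.0) depends on reading the planning values as final scores and on a rounded normal model. If they describe something else, no share follows. A reader might take the illustrated failure rates as expected trial results; they are not.

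**What to change.** In the Assessment section, change the failure condition from a score above 4 to a score of 4 or more (≥4). Success is then 0-3, the mild band, and failure is 4-12, the moderate and severe bands and the entry range. Every attainable score then has one class.

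The cost is one symbol in the protocol and a higher reported failure rate: about 25 points in the nebulizer group and 24 in the inhaler group if the planning values are final scores with SD 1.5. No new data, patients or tests are needed. Which post-treatment assessment the rule applies to, and which children form the denominator, are separate choices that this correction does not settle.

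### A score of exactly 4 escapes the failure definition, and the stopping rule gives no score for improvement

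*Combined protocol and SAP*

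**What the plan says.** In the Assessment section, the response classification is: "Score <4 is considered a success while score>4 is failure of therapy". It stands between the two halves of the treatment rule. The first half is "Patients will be reassessed after each treatment, if improved we can stop treatment and follow up after 2 hrs"; the second is "If not improved, we continue till the maximum number of treatment mentioned above". Neither half gives a score or an amount of change.

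Under Methods of data collection, the score bands are "Mild 0-3 moderate 4-7 severe 8-12", and eligibility is described as "The target population are patients who presented with moderate to severe wheezing (score 4-12").

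The Assessment section lists the comparisons between arms, among them "clinical outcome, patient satisfaction after treatment and hospitalization rate". In the Statistical analysis section, the chi-square entry reads "For categorical variables, to compare between different groups (gender, address, satisfaction, admission"), and the Mann-Whitney entry includes "percentage of improvement of clinical respiratory score and satisfaction". Success or failure of therapy is not named under any test.

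**The concern.** The two inequalities leave out one value, and it is a value that matters. A score of 4 is both the entry threshold and the boundary between mild and moderate. The plainest non-responder at the lower end of eligibility, a child who enters at 4 and is still at 4 after treatment, is therefore not a failure under the written rule. Nor is a child who comes down to 4 from a higher score and is still in the moderate band.

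This is the plan's only classification of clinical response. If it is reported under the listed clinical outcome comparison, the failure rate will be too low by the number of children at 4, or someone will have to settle their label later, possibly with the results known.

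The treatment rule beside it has a related weakness. The likely meaning of *improved* is a score below 4, but the text does not say so, and two clinicians could apply it differently to the same child. When treatment stops can affect the dose received, the treatment time and the final score.

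**Working it through.** **Inputs.** Success is below 4 and failure is above 4 (Assessment). The entry range is 4-12; the bands are mild 0-3, moderate 4-7 and severe 8-12 (Methods of data collection). There are 30 children per arm (Sample size).

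**The plan's own figure.** The arm size reproduces from the stated formula: n = 2 × [(1.96 + 0.84) × 1.5 / (4.4 − 3.3)]² = 29.16, rounded up to 30 per arm. This point does not alter it; 30 serves below only as the denominator.

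**Coverage of the scale.** Six items scored 0, 1 or 2 give whole-number totals from 0 to 12.

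| Score | Below 4 (success)? | Above 4 (failure)? | Class as written |
|---|---|---|---|
| 0-3 | yes | no | success |
| 4 | no | no | none |
| 5-12 | no | yes | failure |

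Of the 13 possible totals, 4 is the only one without a class, and it equals the minimum entry score.

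**Effect per child.** With k children at 4 in an arm of 30, the failure rate as written is too low by k/30. For k = 1 this is 1/30 = 3.3 percentage points; for k = 3 it is 3/30 = 10.0 points.

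**Illustration with assumed counts in one arm of 30:** 15 below 4, 3 at exactly 4, 12 above 4.

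| Rule | Success | Failure | Unclassed |
|---|---|---|---|
| As written | 15/30 = 50.0% | 12/30 = 40.0% | 3/30 = 10.0% |
| Failure defined as 4 or more | 15/30 = 50.0% | 15/30 = 50.0% | 0 |

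Only the failure column moves.

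**Between-arm effect.** If the corrected rule is applied to both arms, the difference in failure rates shifts by (k1 − k2)/30. It is zero when the arms have equal numbers at 4.

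**Named analysis of the score.** Taking percentage improvement as (before − after)/before, a child who enters and ends at 4 contributes (4 − 4)/4 = 0% and stays in the Mann-Whitney comparison.

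**Stopping rule.** The two branches are complements: a child has either improved or not. If improved means below 4, then not improved means 4 or more, and a child at 4 continues. What is missing is the stated score.

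**The case against.** The strongest reply is that the intent is plain and little depends on it. Success is defined without ambiguity, 4 falls in the moderate band and still meets the entry criterion, so a reader would class it as a failure. No named test uses the label, and the score itself is analysed as percentage improvement, where every child counts.

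Most of this stands, and it sets the severity. It does not remove the defect. Followed as written, the rule leaves an unchanged child at the entry threshold out of the failures, and a likely intent is not a pre-specified rule.

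The reply also rules out several stronger readings that a reader might infer:

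- **That the success rate is in doubt.** In the assumed arm above, counting 4 as success would give 18/30 = 60.0%, and leaving those children out would give 15/27 = 55.6%. The first contradicts the written success definition; the second needs an exclusion rule that the plan does not contain.
- **That a child at 4 falls between the two stopping branches.** This requires not improved to mean above 4, which the text does not say.
- **That about a quarter of children would be affected.** A normal approximation with means 4.4 and 3.3 and SD 1.5 puts about 25% and 24% at exactly 4. But the protocol does not say that these planning means are post-treatment scores, so this is no estimate of the number affected.

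**Conclusion.** Wrong as written, and minor. The failure definition omits a score of exactly 4, although a child at 4 is not a success, is in the moderate band and would still qualify for entry. Each such child lowers an arm's reported failure rate by 3.3 percentage points, given 30 children per arm and all of them in the denominator. The success rate, the Mann-Whitney analysis and the sample size are unaffected. The number of children concerned cannot be estimated from the documents and may be none.

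Separately, the stopping rule gives no score for improvement. The position of the threshold sentence suggests below 4, but that is inference. A reader might go further and infer bias towards one arm. The documents do not support this: the same wording applies to both arms, and equal numbers at 4 leave the between-arm difference unchanged.

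**What to change.** Make two wording changes in the Assessment section, identical for both arms:

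1. Define failure of therapy as a score of 4 or more, which agrees with the plan's moderate band and completes the scale.
2. State that improved, in the stopping sentence, means a score below 4, so that not improved means 4 or more.

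No extra patients or form fields are needed, and the sample size stays at 30 per arm. The first change affects only a label. The second has a small cost: staff have less discretion to stop early, and a child who would otherwise have been stopped at 4 or more may receive further doses and reassessments, within the existing maximum for the arm. That could also lengthen treatment duration, which is itself a compared outcome. The rest of the treatment policy can stay as it is.
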